9.2. General Considerations

9.2.1. Definition of Analysis Populations

The Safety population will include all subjects who are randomised and receive at least one dose of investigational product and will be reported by treatment received.

The Intent-To-Treat (ITT) population will include all subjects who are randomised, receive at least one dose of investigational product and have at least one post-baseline efficacy evaluation and will be reported by randomised treatment.

The Per Protocol (PP) population will include all subjects in the ITT population for whom all efficacy assessments are not deemed to be affected by protocol violations.

Protocol violations deemed to affect efficacy will be identified between the Biostatistician and Clinical Research Director or designee, ahead of breaking the study blind.

The primary population for assessment of efficacy will be the ITT population. A PP analysis will be performed on the primary variable only if more than 10% of the subjects in the ITT population have protocol deviations deemed to affect efficacy.

The Safety population will be used for all safety and tolerability reporting.

9.2.2. Exclusion of Data from Analysis

The following will be considered as major protocol deviations leading to the exclusion of subjects / data for PP analysis:

- Deviation from the inclusion/exclusion criteria likely to affect efficacy.

 GlaxoSmithKline	Document Name	207656 Clinical Protocol		
	Type	Version	Document Identifier	Effective Date
	eldo_clinical_doc	3.0; Most-Recent; Effective; CURRENT	090032d580d46916	25-May-2017 00:11:53
	Reason For Issue	Auto Issue		

- The use of prohibited medication likely to affect efficacy.

Other deviations likely to result in exclusion from the PP population will be detailed in the statistical analysis plan (SAP).

9.2.3. Criteria for Evaluation

DH measures captured in the study will be used for efficacy evaluations of the study treatments. OST abnormalities, incidents and AEs reported in the study will be used for safety evaluations of the study treatments.

9.2.4. Criteria for Assessing Efficacy

The primary treatment comparison is between the experimental mouthwash and the negative control marketed mouthwash for the change from baseline in the Schiff Sensitivity score at 8 weeks. However a statistically significant difference is not expected as the study is not powered. The magnitude of the treatment difference is more important and is expected to be in favour of the experimental mouthwash.

9.2.5. Criteria for Assessing Tolerability

The safety profile of the study treatments will be assessed with respect to adverse events (AEs) and oral soft tissue (OST) abnormalities.

9.2.6. Handling of Dropouts and Missing Data

Dropouts and missing data are expected to be low (only 2.3% subjects were discontinued or had missing data after randomisation in the 8 week GSKCH study 204763). A robustness analysis based on worst case imputation might be elaborated in the SAP.

9.3. Statistical Methods and Analytical Plan

Additional details of the proposed statistical analysis will be documented in the statistical analysis plan (SAP), which will be written following finalisation of the protocol and prior to study unblinding.

9.3.1. Demographic and Baseline Characteristics

Descriptive statistics (number of subjects, mean, standard deviation, median, minimum and maximum for continuous variables, and frequency and percentage for categorical variables) will be provided for demographic and baseline data.

 GlaxoSmithKline	Document Name	207656 Clinical Protocol		
	Type	Version	Document Identifier	Effective Date
	eldo_clinical_doc	3.0; Most-Recent; Effective; CURRENT	090032d580d46916	25-May-2017 00:11:53
	Reason For Issue	Auto Issue		

9.3.2. Primary Analysis

The change from baseline to week 8 in the Schiff Sensitivity Score is the primary efficacy variable. This will be analysed using an analysis of covariance (ANCOVA) model. The model will include treatment as a factor and baseline Schiff Sensitivity Score as a covariate.

The primary treatment comparison is between the experimental oral rinse and the marketed oral rinse for the primary efficacy variable. The adjusted mean for each treatment, and the difference between the pair of treatments together with their corresponding 95% confidence intervals and the p-value for treatment comparison, will be provided.

Assumptions of normality and homogeneity of residuals will be evaluated and if serious departures are observed, data transformations will be investigated. If suitable transformations cannot be found, non-parametric tests such as Wilcoxon Rank Sum test or the van Elteren test will be used.

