5.8.1 Randomisation

A unique screening number will identify each subject screened for study participation. Screening numbers will be assigned in ascending numerical order as each subject signs their consent form. Subjects who meet all inclusion and exclusion criteria will be randomised according to the randomisation schedule. Randomisation numbers will be assigned in ascending numerical order as each subject is determined to be fully eligible.

Subjects will be stratified according to their maximum baseline Schiff of the two selected teeth (2/3). Randomisation numbers within each stratum will be assigned in ascending numerical order according to appearance at the study site on the day subjects are randomised. The stratification factor will give rise to two strata.

- **Stratum 1:** Subjects with maximum baseline Schiff sensitivity score of 2 for the two selected test teeth
- **Stratum 2:** Subjects with the maximum baseline Schiff sensitivity score of 3 for the two selected test teeth.

The randomisation list will be prepared using a randomisation block design with a 2:1:1 ratio. The study site will receive two versions of the randomisation schedule, each in a sealed envelope and clearly marked as either “For Dispensing” or “Emergency Use Only”.

The “For Dispensing” schedule will contain the list of randomisation numbers only and will not include any coded description, just a letter A, B or C.

The ‘Emergency Use Only’ randomisation schedule will only be removed from the sealed envelope in an emergency situation (see Section 5.8.3). This schedule will

 GlaxoSmithKline	Document Name	207656 Clinical Protocol		
	Type	Version	Document Identifier	Effective Date
	eldo_clinical_doc	3.0; Most-Recent; Effective; CURRENT	090032d580d46916	25-May-2017 00:11:53
	Reason For Issue	Auto Issue		

have a randomisation number followed by the letter A, B or C. The schedule will be have a footnote with a key for A, B and C identifying the three treatments. However, to maintain the blinding of the study as far as possible, all treatment allocations for all randomisation numbers on this randomisation schedule will be masked with scratch-off panels. Only the panels required for the unblinding the particular subject should be removed.

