9.1 Sample Size Determination

A sufficient number of healthy subjects will be screened to randomise at least 100 subjects (approximately 50 to the experimental treatment, 25 to the negative control and 25 to placebo) to ensure 80 evaluable subjects complete the entire study. This will ensure approximately 40 evaluable subjects for the test treatment and 20 each for the negative control treatment and placebo.

 GlaxoSmithKline	Document Name	207656 Clinical Protocol		
	Type	Version	Document Identifier	Effective Date
	eldo_clinical_doc	3.0; Most-Recent; Effective; CURRENT	090032d580d46916	25-May-2017 00:11:53
	Reason For Issue	Auto Issue		

With this 40/20/20 distribution of the subjects in the treatment arms, the study has less than 50% power to detect a mean treatment difference of 0.36 in the Schiff sensitivity score using a two-sided t-test of significance level 0.05 for the experimental product against the negative control. The standard deviation used in this calculation is 0.8; this estimate is obtained from the GSKCH study 204763. When the experimental treatment group is compared with the combined group comprising of the negative control group and the placebo group using the two-sided t-test with the same estimates of mean difference, significance level and standard deviation, the study will have 51.1% power.

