9.3.3. Secondary Analysis

The change from baseline to week 8 in tactile threshold is the secondary efficacy variable. This will be analysed using an ANCOVA with treatment and baseline Schiff stratification as factors and baseline tactile threshold as a covariate.

The secondary treatment comparison is between the experimental oral rinse and the marketed oral rinse for this variable. The adjusted mean for each treatment, and the difference between the pair of treatments together with their corresponding 95% confidence intervals and the p-value for treatment comparison, will be provided.

Assumptions of normality and homogeneity of residuals will be evaluated and if serious departures are observed, data transformations will be investigated. If suitable transformations cannot be found, non-parametric tests such as Wilcoxon Rank Sum test or the van Elteren test will be used.

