4.4.1.2 Statistical Hypothesis, Model, and Method of Analysis

The primary analysis is a comparison of the mean change from baseline Schiff sensitivity score between Test Product and Negative Control at Week 8.

The null hypothesis for the primary endpoint is that the mean change from baseline in Schiff sensitivity score is equal between the two products.

$$H_0: \mu_1 = \mu_2$$

The alternative hypothesis is that the mean change from baseline in Schiff sensitivity score is not equal between the two products.

$$H_1: \mu_1 \neq \mu_2$$

The change from baseline in Schiff sensitivity score at Week 8 will be analyzed using ANCOVA with treatment as factor and mean baseline Schiff sensitivity score as covariate. Note that since the baseline Schiff sensitivity score will be included as a covariate, the baseline Schiff stratification value will not be included in the model. Adjusted means of all treatments and their SEs, P-value and 95% confidence interval (CIs) will be presented on the ITT population (Table 14.2.1.1.2). Treatment differences of the treatment comparisons will also be provided together with P-values and 95% CIs.

The assumption of normality and homogeneity of variance in the ANCOVA model will be investigated and if violated, data transformations will be investigated. If suitable transformations cannot be found, non-parametric Van Elteren tests will be performed adjusting for the maximum baseline Schiff sensitivity scores and results will be compared with the ANCOVA results. If the inferences from the two analyses are similar then both sets of results will be reported and emphasis will be made on the ANCOVA results. In case of discrepancies between p-values of ANCOVA and Van Elteren analysis, inferences will be drawn on the non-parametric analysis.

To visually inspect the treatment effect on Schiff sensitivity scores, a plot across time (Baseline, Week 4 and Week 8) will be displayed with raw means and SE bars. The plot will display a different symbol line for each treatment group (Figure 14.2.1).

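### The fallback for failed assumptions has no step suited to unequal variances, so with 2:1:1 allocation the test size and the only planned 95% CI for test versus negative control can be off, in either direction

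*Protocol*

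**What the plan says.** Protocol 9.3.2 fits an ANCOVA to the Week 8 Schiff change, with treatment as factor and baseline Schiff as covariate. It then provides: "Assumptions of normality and homogeneity of residuals will be evaluated and if serious departures are observed, data transformations will be investigated". The next step, worded alike in 9.3.2 to 9.3.4, is: "If suitable transformations cannot be found, non-parametric tests such as Wilcoxon Rank Sum test or the van Elteren test will be used".

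SAP 4.4.1.2 narrows the rank test to van Elteren, stratified by maximum baseline Schiff, and adds a rule for choosing between results. When they agree: "If the inferences from the two analyses are similar then both sets of results will be reported and emphasis will be made on the ANCOVA". When the p-values are discrepant, inference rests on the non-parametric analysis. SAP 4.5.1 (tactile threshold) and 4.6 (VRS) repeat the rule.

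No section offers arm-specific variances, robust standard errors or a Welch-type step. The only 95% CI specified is the ANCOVA's; no estimate or interval accompanies the rank test.

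Two other provisions matter. Allocation is unequal: "The randomisation list will be prepared using a randomisation block design with a 2:1:1 ratio". And Protocol 9.2.4 says that significance is not expected and that the size of the treatment difference matters more.

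**The concern.** Non-normality and unequal variance are different failures. A rank test answers the first. It does not in general protect the level of a comparison of means when spreads differ and arm sizes are unequal. The ANCOVA uses one residual variance pooled over three arms, so its standard error for a 40 versus 20 comparison is wrong when those arms differ in variance.

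If the homogeneity check fails and no transformation works, the plan therefore leads to one of two places. One is an emphasised interval built on the variance assumption just rejected. The other is a p-value with no planned interval. Because Protocol 9.2.4 makes magnitude the main result, the interval around the adjusted difference is what readers will use.

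Equal variances cannot be taken for granted. Teeth enter in a narrow range (Schiff 2 or 3, tactile threshold at most 20 g). Later they can reach Schiff 0, or a tactile threshold above 80 g that the SAP scores as 90 g. Later spread may therefore depend on how many subjects respond in each arm.

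**Working it through.** **Inputs from the documents.** Protocol 9.1 supplies the arm sizes ("With this 40/20/20 distribution of the subjects in the treatment arms"), the test ("using a two-sided t-test of significance level 0.05 for the experimental product against the negative control"), the difference (0.36) and the SD: "The standard deviation used in this calculation is 0.8; this estimate is obtained from the GSKCH study 204763". No arm-specific SD is given, so the SD ratios below are assumptions.

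**The plan's own figures reproduce.** Noncentrality is 0.36 / (0.8 × √(1/n₁ + 1/n₂)).
- 40 v 40 (combined control): 2.012, power 51.1%, as stated.
- 40 v 20 (negative control): 1.643, power 36.6%, consistent with the stated figure below 50%.

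**Size of the pooled contrast, test versus negative control.** Let T, N and P denote the test, negative control and placebo arms.
- Pooled variance: s² = (39·T² + 19·N² + 19·P²)/77
- Model SE² = s² × (1/40 + 1/20) = 0.075·s²
- True SE² = T²/40 + N²/20
- r = model SE / true SE; large-sample size = 2·Φ(−1.96·r)

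Example, SDs 1 : 1.5 : 1.5. Here s² = (39 + 42.75 + 42.75)/77 = 1.617. Model SE² = 0.1213 and true SE² = 0.025 + 0.1125 = 0.1375. So r = 0.939 and size = 6.6%.

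| SD ratio T:N:P | s² | Model SE² | True SE² | r | Formula size | Simulated ANCOVA | Simulated van Elteren |
|---|---|---|---|---|---|---|---|
| 1:1:1 | 1.000 | 0.0750 | 0.0750 | 1.000 | 5.0% | 5.3% | 5.3% |
| 1:1.25:1.25 | 1.278 | 0.0958 | 0.1031 | 0.964 | 5.9% | 5.8% | 5.8% |
| 1:1.5:1.5 | 1.617 | 0.1213 | 0.1375 | 0.939 | 6.6% | 6.8% | 7.1% |
| 1:1.5:1 | 1.308 | 0.0981 | 0.1375 | 0.845 | 9.8% | 9.9% | 7.5% |
| 1.5:1:1 | 1.633 | 0.1225 | 0.1063 | 1.074 | 3.5% | 3.8% | 3.9% |
| 1:1:1.5 | 1.308 | 0.0981 | 0.0750 | 1.144 | 2.5% | 2.6% | 5.3% |

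The simulations use no true difference, normal errors, a baseline covariate and two strata. The 1:1.5:1.5 and 1.5:1:1 rows had 15,000 runs and the others 4,000.

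A ratio of 1.25 stays under 6% when both controls share it. If only the negative control has it (1:1.25:1), s² = 87.69/77 = 1.139. Model SE² is then 0.0854 against a true 0.1031, so r = 0.910 and size is 7.45%.

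**Interval coverage** is one minus these sizes: about 93% if both controls have 1.5 times the test-arm SD, about 90% if only the negative control does, and about 96% if the test arm is the more variable.

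**Discrete outcome.** The Schiff mean lies on a half-point grid from 0 to 3. Simulations on that grid, with assumed baseline shares of 40/30/30% at 2/2.5/3, gave for ANCOVA / van Elteren / HC3:
- residual SDs about 0.60/0.85/0.60: 9.1 / 7.1 / 4.6%
- about 0.59/0.80/0.58: 8.0 / 6.6 / 4.8%
- about 0.81/0.59/0.59: 4.0 / 4.0 / 4.7%

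**Combined control.** The contrast weights the two controls one half each. At 1:1.5:1.5, true SE² = 0.025 + 0.25 × 0.225 = 0.08125, against a model value of 1.617 × 0.05 = 0.0808. These are almost equal. Simulated size was 5.1–5.3% in four scenarios: both controls at 1.5 or 2 times the test-arm SD, and the reverse.

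**Remedy.** In those four scenarios, arm-specific variances with Satterthwaite df gave 5.1–5.5% for test versus negative control, and HC3 gave 4.3–4.7%.

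**The case against.** The other side has real points.

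- **The largest figures need an unlikely pattern.** Sizes near 9–10% require the negative control alone to be more variable. Protocol 3.4 describes that rinse as having no known anti-sensitivity activity, so the two controls should behave alike. With both controls more variable the excess is about two points at a ratio of 1.5. This stands, and it sets the expected scale.
- **If spread follows response, equal means imply equal spread.** Under that mechanism there is no Type I inflation. A responder mixture at the planned 0.36 difference (assumed responder gain 1.0–1.5, within-group SD 0.3–0.5, control response 10–50%) gave CI non-coverage of 3.8–5.9%. This limits the likely harm. It does not make the fallback suitable once the homogeneity check has failed.
- **The branch is conditional.** It applies only if a departure is found and no transformation works. A suitable transformation could restore equal variances, and a constant shift handles zero and negative changes, but the estimate would then be on another scale.
- **The study is not powered for significance, and the adjusted difference is not biased by unequal variances.** True. The effect is on the interval's width, which is still the measure of precision for the result the protocol ranks first.

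A reader might infer that the plan always keeps the pooled ANCOVA as headline. It does not. Protocol 9.3.2 moves to a rank test, and the SAP emphasises the ANCOVA only when the two inferences are similar. Simulated runs with unequal variances put the two on the same side of 5% in 95–98% of cases, so that branch would be the usual one.

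**Conclusion.** The gap is real and cheap to close. When the arms being compared differ in variance, the 40 versus 20 primary comparison does not generally keep its 5% level under either planned method, and the only planned interval is mis-sized.

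On assumed SDs, size is about 7% if both controls have 1.5 times the test-arm SD and under 6% at a shared ratio of 1.25. If only the negative control has 1.5 times the SD, it is about 8–10% for ANCOVA and 7–7.5% for van Elteren. If the test arm is the more variable at that ratio, it is about 3–4%.

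Three stronger readings are not supported. The first is that the CI is simply wrong: it is too narrow or too wide depending on which arm varies more, and the documents give no evidence of heterogeneity. The second is that neither method ever holds 5%: if only placebo differs, van Elteren does, while the ANCOVA is conservative. The third is that every comparison is affected: the combined-control contrast is nearly immune.

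**What to change.** In SAP 4.4.1.2, 4.5.1 and 4.6, and in Protocol 9.3.2 to 9.3.4, separate the two failures. If homogeneity of variance fails, fit the same ANCOVA with a residual variance per treatment (in SAS, PROC MIXED with REPEATED / GROUP=treatment and Satterthwaite or Kenward-Roger df) or with HC3 standard errors. Make its adjusted difference and 95% CI, in original units, the emphasised result. Keep transformation and van Elteren for non-normality.

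The cost is wording and one SAS statement, with no new data. If variances are in fact equal, the interval is about 4% wider (simulated half-width 0.441 against 0.424; 0.441/0.424 = 1.04).

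Using this variance structure from the start would also avoid a choice made after unblinding, but that is optional.

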9.3.3. Secondary Analysis

The change from baseline to week 8 in tactile threshold is the secondary efficacy variable. This will be analysed using an ANCOVA with treatment and baseline Schiff stratification as factors and baseline tactile threshold as a covariate.

The secondary treatment comparison is between the experimental oral rinse and the marketed oral rinse for this variable. The adjusted mean for each treatment, and the difference between the pair of treatments together with their corresponding 95% confidence intervals and the p-value for treatment comparison, will be provided.

Assumptions of normality and homogeneity of residuals will be evaluated and if serious departures are observed, data transformations will be investigated. If suitable transformations cannot be found, non-parametric tests such as Wilcoxon Rank Sum test or the van Elteren test will be used.

9.3.4. Exploratory Analyses

Treatment comparisons other than the primary and secondary treatment comparisons mentioned above for the primary efficacy variable are exploratory. These will be performed in the similar way as the primary treatment comparison.

 GlaxoSmithKline	Document Name	207656 Clinical Protocol		
	Type	Version	Document Identifier	Effective Date
	eldo_clinical_doc	3.0; Most-Recent; Effective; CURRENT	090032d580d46916	25-May-2017 00:11:53
	Reason For Issue	Auto Issue		

The change from baseline to week 4 in the Schiff Sensitivity Score will be analysed using the same ANCOVA model as mentioned for the change from baseline to week 8 for this measure.

The change from baseline to week 4 in the tactile threshold will be analysed using the same ANCOVA model as mentioned for the change from baseline to week 8 for this measure.

Changes from baseline to weeks 4 and 8 in VRS will be analysed separately using the similar ANCOVA model as mentioned for the changes from baseline in tactile threshold.

Changes from baseline to weeks 4 and 8 in Schiff Sensitivity Score will further be analysed separately using the same ANCOVA model as mentioned above for this measure but by combining the marketed oral rinse group and the placebo group as one treatment group.

Similar analyses for the combined control group will also be done for the changes from baseline to weeks 4 and 8 for the tactile threshold and VRS using the same ANCOVA model mentioned above for the analysis of the secondary variable.

The adjusted mean for each treatment, and the difference between the pairs of treatments together with their corresponding 95% confidence intervals and the p-values for treatment comparisons, will be provided.

Assumptions of normality and homogeneity of residuals will be evaluated and if serious departures are observed, data transformations will be investigated. If suitable transformations cannot be found, non-parametric tests such as Wilcoxon Rank Sum test or the van Elteren test will be used.

9.3.5. Safety Analyses

For the assessment of safety and tolerability, treatment emergent AEs will be summarised by treatment group. AEs and incidents will be listed. No inferential analyses will be performed to compare treatments with respect to safety data.

The safety profile of the study treatments will be assessed with respect to AEs. OST abnormalities are included as AEs if they appear or worsen after the initial assessment.

 GlaxoSmithKline	Document Name	207656 Clinical Protocol		
	Type	Version	Document Identifier	Effective Date
	eldo_clinical_doc	3.0; Most-Recent; Effective; CURRENT	090032d580d46916	25-May-2017 00:11:53
	Reason For Issue	Auto Issue		

All safety data will be reported for the Safety population as per actual treatment received. All subjects screened will be included in the list of AEs.

All AEs will be reviewed by the Clinical Research Director or Designee prior to database freeze and will be coded using the Medical Dictionary for Regulatory Activities (MedDRA). During this review stage, AEs will be further categorised as oral or non-oral.

AEs will be regarded as treatment emergent if they occur on or after the start date and time of the first treatment usage (as determined by start date and time from the EXPOSURE/dispensing panel; if this date is missing a suitable alternative will be used eg date and time of randomisation). All other AEs prior to this will be considered non-treatment emergent.

The following summary tables and listings will be presented by treatment group.

- Table of treatment emergent AEs by Oral/Non-Oral and Preferred Term
- Table of treatment emergent AEs by SOC and Preferred Term
- Table of Treatment emergent treatment related AEs by Oral/Non-Oral and Preferred Term
- Table of treatment emergent treatment related AEs by SOC and Preferred Term
- Listing of all AEs (including Non-treatment emergent from All Subjects)
- Listing of serious AEs
- Listing of incidents (if there are none a null listing will be produced)

No inferential analyses will be performed to compare treatments with respect to safety.

